## STATEMENT OF COMPLIANCE

The trial will be carried out in accordance with International Council on Harmonisation Good Clinical Practice (ICH GCP) and the following:

- United States (US) Code of Federal Regulations (CFR) applicable to clinical studies (45 CFR Part 46, 21 CFR Part 50, 21 CFR Part 56, 21 CFR Part 312, and/or 21 CFR Part 812).

Investigators and clinical trial site staff who are responsible for the conduct, management, or oversight of clinical trials have completed Human Subjects Protection and ICH GCP Training.

The protocol, informed consent form(s), recruitment materials, and participant materials will be submitted to the Institutional Review Board (IRB) for review and approval. Approval of both the protocol and the consent form(s) must be obtained before any participant is consented. Any amendment to the protocol will require review and approval by the IRB before the changes are implemented to the study. All changes to the consent form(s) will be IRB approved; a determination will be made regarding whether a new consent needs to be obtained from participants who provided consent, using a previously approved consent form.

**1 PROTOCOL SUMMARY****1.1 SYNOPSIS**

Title:	Continuous wearable monitor for the detection and release of freezing of gait.
IRB Number:	A23-354
Study Description:	Proposed is a system (haptic module and insole device) for daily in-community use that detects the occurrence of freezing of gait (FOG) and triggers external cueing stimuli to unfreeze the individual. The purpose of the overall Phase II study is to: (1) Develop a production ready system, (2) Develop a companion mobile app for the proposed system and refine previously developed FOG detection algorithms, and (3) Validate the proper operation of the system and demonstrate its efficacy through lab and in-community testing. This study protocol will focus on validating the system and demonstrating efficacy through in-community testing.
Specific Aims:	Aim 1: Develop production ready insole and charging mat hardware. Aim 2: Refine and implement real-time FOG detection algorithm. Aim 3: Validate the system and evaluate its efficacy with clinical trials. *Note: This protocol will focus on the in-community testing of Aim 3.
Endpoints:	Aim 3 - Primary Endpoint: Duration of FOG events.
Study Population:	36 individuals aged 45 or older with a diagnosis of Parkinson's disease will be recruited for this study to examine Aim 3.
Description of Sites/Facilities Enrolling Participants:	Participants will be enrolled at Struthers Parkinson's Center and HealthPartners Neuroscience Center for Aim 3.
Description of Study Intervention/Experimental Manipulation:	Participants will use the wearable haptic module and insole device for a duration of 5 weeks within their home and the community. Data will be recorded by the device.
Study Duration:	The total duration of this study is 1 year.
Participant Duration:	Participants should be able to complete all study-related tasks within approximately 7 weeks, depending on scheduling of the pre- and post-treatment visits.

## 1.2 SCHEMA

## 1.3 SCHEDULE OF ACTIVITIES

	Pre-screening Phone Call	Pre-treatment Visit	Study Intervention	Post- treatment or Early Withdrawal Visit
	Visit 1	Visit 2	5 weeks	Visit 3
Review Eligibility	X			
Informed Consent		X		
Demographics		X		
Medication tracking		X		X
Device Training		X		
Device Return				X
2-minute walk test		X		
New Freezing of Gait Questionnaire (NFOG-Q)		X		X
Characterizing Freezing of Gait Questionnaire (CFOG-Q)		X		
Falls Questionnaire		X		
Structured Interview				X
Weekly phone call			X	
Adverse Events (AE) Reporting			X	X
Treatment Adherence			X	
Daily FOG diary			X	

#### **1. Pre-screening Phone Call**

- Duration: Approximately 30 minutes via phone
- Research staff will:
  - Provide potential participants information about the study and ask whether they are interested in participating.
  - Determine whether they meet the inclusion/exclusion criteria for the study.
  - Ask for permission to communicate through e-mail for the study (e.g., for scheduling purposes).
  - Schedule the Pre-treatment Visit if the person is eligible for the study and e-mail them the Informed Consent and Health Insurance Portability and Accountability Act (HIPAA) forms.

#### **2. Pre-treatment Visit**

- Duration: Approximately 120 minutes in person
- Research staff will:
  - Review the Informed Consent and HIPAA documents with participants.
  - Answer any questions of participants and ensure they understand the expectations of the study.
  - Ask participants to sign the Informed Consent and HIPAA documents and provide them copies for their records.
  - Complete baseline assessments/questionnaires (2-minute walk test, NFOG-Q, CFOG-Q, Falls Questionnaire).
  - Train participants on how to use the haptic module and insole device and provide instructions for the daily FOG diary.

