#### **3. Study Intervention**

- Participants will wear the haptic module and insole device as often as possible for 5 weeks within their home and the community. They will also complete a daily FOG diary.
- Research staff will:
  - Call participants weekly to check in regarding any issues with the device and complete the AE/SAE reporting form in REDCap (approximately 15-30 minutes).

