#### **4. Post-treatment Visit**

- Duration: Approximately 60 minutes in person
- Research staff will:
  - Complete the AE/SAE reporting form in REDCap.
  - Complete NFOG-Q and structured interview with the participant.
  - Receive the device from participants and return it to the sponsor.

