### Haptic Module & Insole Device

The developed system consists of the sensing insole and the electronics enclosure. The insole slides into the subject's shoe, underneath their existing shoe insole (if removable) and connects to the electronics enclosure through a physical cable. The electronics enclosure clips onto the exterior side of the subject's shoe. The system will be designed to minimize volume (e.g., the insole is <1mm thick) and avoid any hard components in the shoe. Similar systems have been tested by Innovative Design Labs (e.g., RxFunction Walkasins and PhySens-IMM) and found to be a non-significant risk device. The Haptic Module wraps around the lower leg and can be worn on top of the clothing for comfort.

Potential risks of wearing the haptic module and insole device include:

- Foot/ankle pain or discomfort
- Skin irritation or wounds
- Falls

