#### 6.1.2 ADMINISTRATION AND/OR DOSING

The main purpose of this study is to establish the robustness and efficacy of the haptic module and insole device through long-term, continuous use while subjects proceed with their activities of daily living at home and in the community. Data will be collected in three parts. Part 1 will collect data for 7 days with the cueing intervention turned off to establish a baseline. Part 2 will collect data over 21 days with the cueing intervention turned on. Part 3 will examine the wash-out effects of cueing by collecting for an additional 7 days with the cueing intervention turned off. Throughout this trial, daily dairies of FOG episodes, user impressions, and adverse events will be collected. Data from the insole will automatically (no participant interaction for the duration of the study) be downloaded by the charging mat's nRF52840

BLE radio/processor and stored to a secure digital card. Participants will be contacted weekly by the research coordinator to discuss use of the device and compliance with protocol.

The sensing device consists of two parts for each leg: the Haptic Module and the Insole (Figure 1). The Haptic Module wraps around the lower leg (Figure 2) of the user and contains electronics for wireless communication, a microprocessor, and four vibrating motors that provide gentle tactile sensory cues to the front, back, medial, and lateral surfaces of the user's leg when a FOG event is detected. The Haptic Module has a power button, two status LEDs, and a reset button. Power is supplied by a rechargeable internal battery.

The Insole is a pressure-sensitive insert that fits in a regular shoe with a battery and electronics for sampling pressure measurements. The electronics are housed in a sealed plastic case that securely clips to the outside of the wearer's shoe (Figure 2). The insole has a single status light and no buttons. Users recharge the insole and haptics module via USB connectors.

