# 8 STUDY ASSESSMENTS AND PROCEDURES

## 8.1 ENDPOINT AND OTHER NON-SAFETY ASSESSMENTS

**Demographics:** Demographic information will be collected, including gender, age, race, ethnicity, height, weight, marital status, and employment status.

**Protected health information collected:** Name, medical record number, birth date, phone number, address, email address, and medical history, including date of PD diagnosis.

**New Freezing of Gait Questionnaire (NFOG-Q):** The NFOG-Q is a self-report questionnaire with 9 items that measure FOG.

**Characterizing Freezing of Gait Questionnaire (C-FOGQ):** The C-FOGQ is a self-report questionnaire that provides insights into the triggers of freezing.

**Falls Questionnaire:** The falls questionnaire is a 4-item self-report survey including questions about any recent falls. The questionnaire was developed by the [name] at the University of Minnesota.

**FOG Diary:** Participants will be provided paper diaries to keep track of their FOG events and will be asked to report the information during the weekly phone call for the 5-week intervention.

**Adherence:** The participant's adherence to using the haptic module and insole device will be measured. Daily use of the device will be recorded during the weekly phone call for the 5-week intervention.

**Structured Interview:** Participants will be asked to complete a structured questionnaire at the post-treatment visit. The interview will include questions about their experience with using the device within their home and community.

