#### 8.3.4 TIME PERIOD AND FREQUENCY FOR EVENT ASSESSMENT AND FOLLOW-UP

The occurrence of an AE or SAE may come to the attention of study personnel during study visits and interviews of a study participant.

All AEs, not otherwise precluded per the protocol, will be captured on the appropriate eCRF. Information to be collected includes event description, time of onset, clinician's assessment of severity, relationship to study procedures (assessed only by those with the training and authority to make a diagnosis), and time of resolution/stabilization of the event. All AEs occurring while on study will be documented appropriately regardless of relationship. All AEs will be followed to adequate resolution.

Any medical or psychiatric condition that is present at the time that the participant is screened will be considered as baseline and not reported as an AE. However, if the study participant's condition deteriorates at any time during the study, it will be recorded as an AE.

Changes in the severity of an AE will be documented to allow an assessment of the duration of the event at each level of severity to be performed. Documentation of onset and duration of each episode will be maintained for AEs characterized as intermittent.

Study staff will record events with start dates occurring any time after study enrollment until study completion. At each in-person visit or phone call, study staff will inquire about the occurrence of AE/SAEs since the last inquiry. All reported events will be monitored until resolution or study completion. Any reported event that is definitely or probably related to the intervention will be followed until resolution or stabilization.

---

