#### 9.4.4 SAFETY ANALYSES

AE/SAEs will be reported as described in section 8.3 of this document. They will be classified by severity, relationship to study procedures, and expectedness. No other formal safety analyses will be conducted.

---

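### Falls are a listed device risk, but after baseline they are not counted in a structured way or compared by cueing state, so a rise under cueing could be under-recorded or go unrecognised

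*Combined protocol and SAP*

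**What the plan says.** In Section 2.2.1, under the haptic module and insole device, the sentence beginning "Potential risks of wearing the haptic module and insole device include" is followed by three bullets, the third of which is falls.

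The falls instrument is described in Section 8.1: "The falls questionnaire is a 4-item self-report survey including questions about any recent falls". No recall window is given. The Schedule of Activities (Section 1.3) marks it once, at Visit 2, and the pre-treatment visit text agrees: "Complete baseline assessments/questionnaires (2-minute walk test, NFOG-Q, CFOG-Q, Falls Questionnaire". The post-treatment visit does not repeat it: "Complete NFOG-Q and structured interview with the participant". The early withdrawal visit has the same content on this point.

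AEs are collected more often. During the five weeks staff will "Call participants weekly to check in regarding any issues with the device and complete the AE/SAE reporting form in REDCap". Section 6.1.2 adds that "daily dairies of FOG episodes, user impressions, and adverse events will be collected". Section 8.3.4 says "Information to be collected includes event description, time of onset", and requires AEs to be documented whatever their relationship to the study.

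Section 8.3.1 takes its AE definition from the federal regulation (an untoward medical occurrence) and does not mention falls. Section 8.3.8, on events of special interest, is marked not applicable. Section 9.4.4 classifies events by severity, relationship and expectedness, and then closes: "No other formal safety analyses will be conducted".

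Cueing is off in week 1, on in weeks 2 to 4 and off in week 5 (Sections 6.1.1 and 6.1.2). Section 10.1.6 has an independent data safety officer review accumulating safety data for trends, under a separate data safety monitoring plan.

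**The concern.** Participants freeze while walking, and the device delivers a vibration to the leg when it detects a freeze. Whether people fall more often with cueing on is the obvious safety question. The off-on-off schedule could give some information on it at almost no cost. The plan does not secure that information, for two reasons.

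- **Capture.** It is left to judgement whether an uninjured fall is an AE, so two staff members could treat the same fall differently. Section 8.3.4 also treats conditions present at screening as baseline unless they deteriorate, and gives no rule for someone who already falls regularly.
- **Analysis.** Events from cued and uncued weeks go into the same classification, with no denominators.

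A reader of the final report could then see a list of falls and be unable to say whether cueing made them more or less frequent.

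**Working it through.** The plan gives no figure for falls, so there is none to reproduce. The check has three parts.

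**1. From the listed risk to the report.** Falls are listed in Section 2.2.1. The Falls Questionnaire is given at Visit 2 only, so it supplies no data on the intervention period. Dated AEs can be assigned to a cueing period, because switching occurs at the ends of weeks 1 and 4. No section requires that assignment, and no section says which falls are AEs. Section 6.1.2 says the diaries collect AEs, whereas Section 8.1 describes the diary only as a record of freezing events. Neither specifies an entry for falls.

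**2. Why raw totals mislead.** Cued time is 21 days and uncued time is 7 + 7 = 14 days. With equal fall rates, cued falls / uncued falls = 21/14 = 1.5. A tally of 15 cued and 10 uncued falls would show no difference in rate.

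**3. How precise a rate comparison would be.** Inputs from Section 9.2: 36 recruited, 29 required for analysis. With full follow-up of 36 people:

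- uncued person-weeks: 36 × 2 = 72
- cued person-weeks: 36 × 3 = 108

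The uncued fall rate r is an assumption, shown over a range. For an observed doubling, uncued falls a = 72r and cued falls b = 108 × 2r. Treating the counts as simple Poisson, SE(log rate ratio) = √(1/a + 1/b), and the 95% interval is 2 × exp(±1.96 × SE).

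| Assumed r (falls per uncued person-week) | a | b | SE | 95% interval around 2.0 |
|---|---|---|---|---|
| 0.05 | 3.6 | 10.8 | 0.609 | 0.61 to 6.59 |
| 0.10 | 7.2 | 21.6 | 0.430 | 0.86 to 4.65 |
| 0.25 | 18 | 54 | 0.272 | 1.17 to 3.41 |

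Two variations:

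- **Attrition.** With 29 people (58 uncued and 87 cued person-weeks) the intervals become 0.53 to 7.55, 0.78 to 5.12 and 1.10 to 3.62.
- **Week 1 alone as the reference.** With 36 people, a = 36r and b is unchanged. The intervals become 0.41 to 9.69, 0.66 to 6.10 and 0.99 to 4.05.

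Falls that cluster in a few repeat fallers would widen all of these.

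**The case against.** The strongest reply is that the plan is not blind to falls. AEs are asked about every week, recorded with onset time regardless of relationship, and reviewed for trends by an independent officer. Section 8.3.3.3 makes an event unexpected if its frequency departs from the described risk, which gives a further informal route. A reader might infer from the baseline-only questionnaire that a rise in falls would certainly be missed, that the within-person comparison is thrown away, or that the safety officer sees only totals. The documents support none of these. The dated AE data would allow a later tabulation of the falls that were reported. What the officer receives is left to a monitoring plan that is not among these documents. The frequency route is weak, however, because Section 2.2.1 gives no expected frequency to compare against.

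Other parts of the reply stand:

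- The baseline questionnaire fits its stated use, which is to describe the population (Section 9.4.1). Repeating it at Visit 3 would not isolate cueing, because that visit follows an uncued week and the recall window is not stated.
- The listed risk is that of wearing the device, which is also worn in weeks 1 and 5. An on/off contrast addresses the effect of cueing, not of wearing.
- Period is confounded with time, wear time will vary, and week 5 is there to study wash-out, so pooling it with week 1 assumes no carry-over.
- If remote switching fails, Section 6.1.1 has the devices unworn in weeks 1 and 5, so those participants have no device-worn uncued reference.
- A planned contrast could itself fail to show a doubling unless falls are frequent.

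These points limit what the comparison can prove. They do not justify leaving it unspecified.

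**Conclusion.** The point holds in a limited form. Falls are a named risk with no structured count after baseline, no rule on whether an uninjured fall is an AE, and no planned comparison by cueing state. A rise under cueing could therefore be under-recorded or go unrecognised. The documents do not show that it would be.

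The 1.5-fold imbalance in raw counts follows from the schedule alone, taking equal rates and equal follow-up in each period. The intervals rest on assumed fall rates and independent Poisson counts, and pooling weeks 1 and 5 also assumes no carry-over. At 0.05 or 0.10 falls per uncued person-week, the interval around an observed doubling includes 1. At 0.25 it excludes 1 with both uncued weeks pooled, and just includes it with week 1 alone. The comparison is worth having as description, not as a test. The primary analysis is unaffected.

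**What to change.** 1. At the existing weekly call, record the number and date of all falls since the last call, injurious or not. State in Section 8.3 when a fall is to be recorded as an AE, including for participants who already fall at baseline.
2. In Section 9.4.4, replace the closing sentence with a descriptive table of falls and device-related AEs per person-week (per hour worn, where available) for week 1, weeks 2 to 4 and week 5. Assign time by actual cueing state, and keep week 5 separate because it is the wash-out week. Give a rate ratio with an interval that allows for repeat fallers, for example from a negative binomial model or a bootstrap that resamples participants. State whether the reference is week 1 alone or both uncued weeks.
3. Give the same table to the data safety officer, and refer to it in the data safety monitoring plan.

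Repeating the Falls Questionnaire at Visit 3 is not needed for this purpose.

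The cost is one added item per weekly call, one table and a short amendment for IRB approval, with no extra visit or staff. The drawback is low precision, so the text should say in advance that the table is descriptive and that a wide interval is not evidence of safety.

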#### **3. Study Intervention**

- Participants will wear the haptic module and insole device as often as possible for 5 weeks within their home and the community. They will also complete a daily FOG diary.
- Research staff will:
  - Call participants weekly to check in regarding any issues with the device and complete the AE/SAE reporting form in REDCap (approximately 15-30 minutes).

#### **4. Post-treatment Visit**

- Duration: Approximately 60 minutes in person
- Research staff will:
  - Complete the AE/SAE reporting form in REDCap.
  - Complete NFOG-Q and structured interview with the participant.
  - Receive the device from participants and return it to the sponsor.

#### **5. Early Withdrawal Visit**

- Duration: Approximately 60 minutes in person
- Research Staff will:
  - Record the reason for study withdrawal.
  - Complete the AE/SAE reporting form in REDCap.
  - Complete NFOG-Q and structured interview with the participant.
  - Receive the device from participants and return it to the sponsor.

## 2 INTRODUCTION

### 2.1 BACKGROUND & STUDY RATIONALE

Parkinson's disease (PD) affects more than one million Americans, and its prevalence is expected to double by 2040. Among the most treatment-resistant motor symptoms is freezing of gait (FOG). FOG is defined as “an episodic inability (lasting seconds) to generate effective stepping in the absence of any known cause other than Parkinsonism or high-level gait disorders”. This symptom affects more than 30% of all participants with PD and is characterized by episodic impairments in the ability to initiate gait and the spontaneous arrest of movement during stepping. Incidence of FOG increases with severity and duration of PD with 80% of severely affected participants reporting freezing. Episodes last from a few seconds to up to one minute and can be triggered by turning, approaching a narrow doorway or obstacles, or seemingly nothing in particular. The incidence and severity of FOG episodes increases with disease progression. While levodopa and deep brain stimulation can often reduce the incidence and duration of FOG episodes, the efficacy of these treatments generally decreases over time.

Clinicians have long recognized that one of the best methods to facilitate movement initiation in participants with PD is to provide them with a sensory cue (e.g., visual, acoustic, or somatosensory). Performance following a cue is often equivalent to, or greater than, that observed with levodopa replacement therapy. Existing products that provide cueing such as the LaserCane either use a continuous signal or periodic metronome-like signal, however, their effectiveness diminishes quickly over time. It has recently been shown that the reliability and effectiveness of external cueing is critically dependent upon the timing and method of presentation of the stimulus. If the external stimulus is self-triggered (e.g., via button press, as is done in most commercially available cueing systems), the cue is ineffective in improving gait initiation. If the cue is exogenously presented, the incidence of an inappropriate gait initiation sequences is reduced from 20% to less than 1% and the magnitude of force generation during stepping increases by an average of 45-71%.

In this Phase II study, a system (haptic module and insole device) is being developed for daily in-community use that detects the occurrence of FOG and triggers external cueing stimuli to unfreeze the individual. IDL and its collaborators propose to: (1) Develop a production ready system, (2) Develop a companion mobile app for the proposed system and refine previously developed FOG detection algorithms, and (3) Validate the proper operation of the system and demonstrate its efficacy through in-lab and in-community testing. **This study protocol describes testing the usability and efficacy of the system in people with Parkinson’s disease within their home and community (Aim 3; In-community testing).**

